5.3 Sample Size

This is a randomized, controlled, double-blind, multicenter, superiority-designed phase III clinical study. Assuming that a PFS hazard ratio (HR) of HS-10296 to gefitinib is 0.67 (median PFS will be improved from 10 months to 15 months if the data meet the exponential distribution and statistical model meets the proportional hazard assumption), with the randomization ratio of 1:1, an enrollment duration of 8 months, a maximum observation period of 23 months after the first patient is enrolled, a two-sided alpha of 0.05, and with a power of 90% to detect the statistical differences between the two groups based on 262 events, approximately 410 patients need to be enrolled. The sample size is calculated by nQuery Advisor 8.0 software.

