12.1.3 Progression-free Survival (PFS)

According to RECIST 1.1 ([Appendix D](#)), PFS is defined as the time period from the randomization to the occurrence of objective tumor progression assessed by the Investigator or death. In the absence of disease progression, radiographic tumor assessments will need to be collected until RECIST-defined disease progression, even if the patient has discontinued the treatment with HS-10296 or has received another anti-tumor therapy prior to disease progression.

A subject who does not have disease progression or is dead at the time of analysis will be censored at the last date of his/her last assessment as per the RECIST criteria. If a subject

experiences disease progression or death after 2 or more missing visits, the subject will be censored at the last date of his/her last assessment as per the RECIST criteria. The data derived from the progression-free survival are based on assessment date rather than visit date.

If a patient discontinues study treatment prior to progression and/or receives other treatments prior to progression, the patient will be continued to be followed up until evidence of objective disease progression as per RECIST 1.1. Worsening of symptoms will not be considered as an event of progression.

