#### 4. Analysis of efficacy

##### 4.1. Primary Efficacy Endpoint Analysis

The primary efficacy endpoint of this study is PFS as evaluated by the investigator. The primary analysis is based on the full analysis set. For the rules for determining the dates of progression when the subjects have disease progression during treatment, see [Table 4.1-1](#). For the primary event censoring rules, see [Table 4.1-2](#).

Table 4.1-1 Rules for determining the date of progression when there is disease progression

	Description of situation	Outcome (occurrence of event or censoring)	Date of occurrence of PFS event or end date
Progression confirmed during treatment	New lesions	Progression	Date of imaging examination during which new lesions were first found (if the criterion for progression is new lesions)
	Non-target lesions	Progression	Date of last imaging examination during which progression of non-target lesions was first found
	Target lesions	Progression	Date of last imaging examination during which progression of target lesions was first confirmed
When two or more are present, the corresponding dates are determined based on the above principles and compared. Finally, the earliest examination date is taken as the date of disease progression			

Table 4.1-2 PFS event censoring rules 1 (primary event censoring rules)

Situation	Date	Outcome
No baseline or post-baseline imaging evaluation results	Date of randomization	Censored
No progression or death before data cutoff	Date of the last valid imaging examination before data cutoff	Censored
Treatment terminated or new systemic tumor therapy started before non-imaging disease progression	Date of the last valid imaging examination before the termination of treatment or the start of new systemic anti-tumor therapy	Censored
Disease progression or death before data cutoff (including occurrence during a missing visit or unplanned visit)	Examination date of first imaging disease progression or date of death	Progression or death

Progression or death occurred before data cutoff but two or more consecutive visits are missing or evaluation could not be performed before progression or death	Date of last valid imaging examination before progression or death	Censored
Note: No baseline is when there are no baseline examination records or baseline target lesion examinations are missing.		

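### The missed-assessment censoring rule for primary PFS differs between protocol and SAP, and neither text ties the gap to the time immediately before the event

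*SAP*

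**What the plan says.** **Protocol 12.1.3** defines PFS from randomization to investigator-assessed progression or death. A subject who "experiences disease progression or death after 2 or more missing visits, the subject will be censored" at the last RECIST assessment. The text says nothing about whether the missed visits must be consecutive or where they must fall relative to the event.

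**SAP 4.1, Table 4.1-2** (primary censoring rules) has two relevant rows.
- Row 4 counts an event: "Disease progression or death before data cutoff (including occurrence during a missing visit or unplanned visit").
- The last row censors when progression or death occurred before cutoff but "two or more consecutive visits are missing or evaluation could not be performed before progression or death". The censoring date is the last valid scan before the event.

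**SAP section 6** lists one change from the protocol, the start date for overall survival. The added word *consecutive* is not listed.

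**SAP 2.2.9** treats scans that are missing or not evaluable because of COVID-19 as missing under these rules.

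**SAP Table 4.2-1** (secondary censoring rules) has no missed-visit row. The output list plans Table 14.2.4.1, investigator PFS under those secondary rules. The bullet in SAP 4.2 that appears to correspond, the re-analysis in the full analysis set, names the primary rules instead.

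**The concern.** This rule decides which progressions and deaths count in the primary test, and the wording allows three readings:

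1. **Anchored:** two or more consecutive assessments missed immediately before the event.
2. **Literal SAP:** two consecutive assessments missed at any time before the event.
3. **Literal protocol:** any two assessments missed before the event.

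Take a patient who misses the week 12 and week 18 scans, has stable disease on every scan from week 24 to week 54, and progresses at week 60. The progression is located to within one scan interval. The anchored reading counts it. Either literal reading censors it at week 54.

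It is also unclear whether one assessment that could not be evaluated triggers the SAP row, or whether two are needed.

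The stakes are the event count, the power and the Kaplan-Meier rates. An event censored at the last progression-free scan pushes the estimated curve up. Two programmers following the two documents could produce different primary event counts.

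**Working it through.** **Design inputs (protocol 5.3).** "Assuming that a PFS hazard ratio (HR) of HS-10296 to gefitinib is 0.67"; "median PFS will be improved from 10 months to 15 months" under exponential PFS; "with the randomization ratio of 1:1"; "a two-sided alpha of 0.05"; "with a power of 90% to detect the statistical differences between the two groups" on 262 events; about 410 patients; 8 months of accrual; 23 months in total.

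**Step 1: reproduce the plan's figures.**
- Events (Schoenfeld): 4 × (1.960 + 1.282)² / (ln 0.67)² = 262.06. The stated 262 reproduces, and power at 262 events is 89.99%.
- Event probability by 23 months: P = 1 − (e^(−15λ) − e^(−23λ)) / (8λ), with λ = ln 2/10 for gefitinib and 0.67 × ln 2/10 for HS-10296. This gives 0.729 and 0.584, mean 0.656.
- 262 / 0.656 = 399 patients, within 3% of 410. Conversely, 410 × 0.656 = 269 events.

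**Step 2: simulate the three readings.** Scans follow the protocol schedule: 6-weekly through C21, then C23 and 12-weekly after that. Progression is recorded at the first attended scan on or after its true time. With 205 patients per arm this gives about 256 recorded events by month 23, fewer than 269 because of the wait for the next scan. Each scan is missed independently with a fixed probability. That probability is an assumption, since the documents give none. There is no dropout.

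Share of recorded events censored, both arms combined:

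| Missed-scan rate | Anchored | Literal SAP | Literal protocol |
|---|---|---|---|
| 2% | 0.1% | 0.2% | 0.7% |
| 5% | 0.6% | 1.4% | 4.0% |
| 10% | 2.3% | 5.0% | 12.5% |
| 15% | 5.0% | 10.5% | 22.5% |

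Applied to about 256 events, the 5% and 10% rows give about 2 and 6 events censored (anchored), 4 and 13 (literal SAP), and 10 and 32 (literal protocol).

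**Step 3: convert to power at 10% missed.** Power = Φ(√d / 2 × |ln 0.67| − 1.960), with |ln 0.67| = 0.4005. For example, d = 225 gives 7.5 × 0.4005 − 1.960 = 1.044, so 85.2%.

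| Reading | Events counted | Power |
|---|---|---|
| No such rule | 256–257 | 89.3–89.4% |
| Anchored | 250–251 | 88.6–88.7% |
| Literal SAP | 243–244 | 87.7–87.9% |
| Literal protocol | 224–225 | 85.0–85.2% |

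The ranges reflect rounding and simulation error of about one event.

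**Step 4: direction.** Under the literal protocol reading at 10% missed, the censored share is 12.0% of gefitinib events and 13.2% of HS-10296 events. The shares are close, so equal missingness costs events and gives no reason to expect a biased hazard ratio. The Kaplan-Meier rates do move: 18-month PFS rises by about 0.06 in each arm under that reading (about 0.29 to 0.35 for gefitinib, about 0.44 to 0.50 for HS-10296).

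**The case against.** **An anchored reading is available.** The SAP censors at the last valid scan before the event. That is most natural when the gap runs up to the event, because that scan is then the one before the gap. The odd result in the week 60 example also counts against the literal reading. This stands, so a reader should not infer that the plan does discard validly observed progressions. It permits their censoring if followed literally. Nor does the protocol say that any two visits suffice; it is silent on spacing.

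**Visits could be taken as clinic visits.** Clinic visits are 3-weekly up to C7 and scans are 6-weekly, so a reader might infer that two missed clinic visits with only one scan due would trigger the rule. The documents do not support that. SAP 2.2.8.1 applies Table 4.1-2 when tumor assessment results are missing, SAP 2.2.9 speaks of tumor evaluations, and protocol 12.1.3 bases PFS on assessment dates.

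**Row 4 and the last row might seem to conflict.** The word *but* in the last row makes it an exception to row 4. A note on precedence is only an editorial help.

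**A sensitivity analysis restores the events.** Table 14.2.4.1 would show the effect of dropping the rule. This stands in part: the SAP 4.2 bullet names the primary rules, so the safeguard is itself inconsistent. A sensitivity analysis also does not settle what the primary analysis is.

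**The effect is small.** The SAP is the operative analysis document, and its literal wording differs from the anchored rule by only about 2 to 7 events and less than one power point at 5–10% missed. This stands. The power figures also assume a fixed 23-month cutoff; if the analysis waits for 262 counted events, the cost is time.

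**Conclusion.** The point holds as a conflict and an ambiguity in the primary-endpoint rule. The two documents state different conditions, the difference is undeclared, and neither anchors the gap to the event.

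At an assumed 5–10% missed-scan rate, the anchored rule censors about 2–6 of roughly 256 events, the literal SAP wording about 4–13 and the literal protocol wording about 10–32. At 10%, power is about 88.7%, 87.8% and 85.2%, against 89.4% with no such rule. The larger losses belong to the literal protocol wording.

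These sizes rest on independent misses at a constant rate, equal in both arms, with no dropout. Clustered misses, such as COVID-19 could cause, would raise the counts under the two readings that need consecutive misses. A reader might infer that the rule favors one arm; the calculation does not show that when missingness is equal by arm.

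The texts should be corrected because the rule governs the primary analysis and the correction is nearly free, even though the likely numerical effect is modest.

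**What to change.** 1. **SAP Table 4.1-2, last row.** Replace with: *If progression or death occurs immediately after two or more consecutive scheduled tumor assessments that were missed or not evaluable, censor at the last evaluable assessment before that gap; otherwise count the event.* Note that this row is an exception to row 4. The wording also settles that a single non-evaluable scan is not enough.
2. **State the gap in days for both schedules.** One way is two scan intervals plus the ±7-day window at each end: 2 × 42 + 14 = 98 days on the 6-week schedule, 2 × 84 + 14 = 182 days on the 12-week schedule, and 42 + 84 + 14 = 140 days across the change.
3. **SAP section 6.** Declare the difference from protocol 12.1.3, and align the protocol text at the next amendment.
4. **SAP 4.2.** Correct the re-analysis bullet to name the secondary censoring rules, so that it matches Table 4.2-1 and Table 14.2.4.1.

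The cost is a few lines of SAP text and a small change to the PFS derivation program, with no new data. SAP 2.2 has the plan finalized before data lock, so the change belongs before then. Holding the protocol wording for the next amendment avoids a separate ethics submission.

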#### 4.2. Sensitivity Analysis of the Primary Efficacy Endpoint

The following sensitivity analysis is performed on the primary efficacy endpoint:

- Considering the presence of primary resistance to EGFR TKI in non-small cell lung cancer patients with sensitive EGFR mutations, the early progression data may not satisfy the statistical assumptions of proportional hazards. The primary event censoring rules will be adopted to analyze the data of patients with primary drug resistance removed from the primary efficacy endpoint (progression within 3 months) in the full analysis set
  - The primary event censoring rules are used for analysis of the main efficacy endpoint in the per-protocol set
    - The primary event censoring rules are used for analysis of the main efficacy endpoint minus 42 days of patients with disease progression after 15 months in the full analysis set
    - The primary event censoring rules are used for re-analysis of the main efficacy endpoint based on the full analysis set
  - The primary event censoring rules are used for analysis of the PFS results derived by IRC evaluation based on the full analysis set
  - Based on the primary event censoring rules, subjects for whom the main efficacy endpoint is evaluated as "NE" before progression because of the epidemic are censored to the date on which the evaluation result before disease progression is "NE" for sensitivity analysis

Table 4.2-1PFS event censoring rules 2 (secondary event censoring rules)

Situation	Date	Outcome
No baseline or post-baseline imaging evaluation results	Date of randomization	Censored

No progression before data cutoff	Date of the last valid imaging examination before data cutoff	Censored
Progression or death before data cutoff	Examination date of first imaging disease progression or date of death	Progression or death

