6.0 Study Design and Description

6.1 Study Design

This is a randomized, controlled, double-blind, multicenter, phase III clinical trial to evaluate the efficacy and safety of HS-10296 versus gefitinib as the first-line therapy in subjects with EGFR^{mut} NSCLC who have not received any systemic therapy. Patients will be randomized in a 1:1 ratio to HS-10296 treatment group or gefitinib treatment group to receive oral administration of HS-10296 or gefitinib once daily. It is planned to enroll 410 subjects in the study, and the study flow chart is shown in Figure 1.

[figure not shown]

Figure 1 Study Flow Chart

● Screening Period (D-28 to D-1)

Inpatients and outpatients will be screened after signing the informed consent form, and complete relevant laboratory tests and assessments. Subjects who meet the inclusion criteria and do not meet the exclusion criteria may be enrolled.

● Treatment Period (C1 to C7 +, D1 to D127 +)

All eligible subjects will be randomized in a 1:1 ratio to the following two groups:

- 1) HS-10296 group: oral administration of 110 mg HS-10296 tablets (55 mg/tablet, 2 tablets/d) and gefitinib placebo tablets (placebo 250 mg, 1 tablet/d) once daily for 21 consecutive days (3 weeks) as one cycle.
- 2) Gefitinib group: oral administration of 250 mg gefitinib tablets (250 mg/tablet, 1 tablet/d) and HS-10296 placebo tablets (placebo 55 mg, 2 tablets/d) once daily for 21 consecutive days (3 weeks) as one cycle.

The drugs will be administered for 21 consecutive days, which constitute one treatment cycle. Response will be evaluated as per RECIST 1.1 every 6 weeks (every 2 cycles until C21; first 15 months) or every 12 weeks (every 4 cycles starting from C23; after Month 15) after initiation

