Appendix B Study Plan

• Study Plan for Randomized Treatment													
Visit ^a	Screening Period	Treatment Period								Study Discontinuation Follow-up	Follow-up Period		
		1	2	3	4	5	6	7-9	10+		28-day follow-up ^b	Progression Follow-up Every 6/12 weeks	Survival Follow-up Every 6 weeks
Treatment cycle ^c /day		C1 D1	C1 D8	C1 D15	C2 D1	C3 D1	C4-C6 D1	D1 of C7 and Every 6/12 weeks thereafter		NA	NA	NA	NA
Day	-28	1	8	15	22	43	64-106	127+		NA	NA	NA	NA
Window period (days)	NA	0	±2	±2	±2	±7	±7	±7		+7	NA	±7	±7
Informed consent	×												
Demographic and baseline characteristics	×												
Medical/surgical history	×												
Inclusion/exclusion criteria	×												
EGFR mutation test	×												
Physical examination (including body weight) ^d	×	×			×	×	×	×	×				
Body Height	×												
ECOG PS score	×	×			×	×	×	×	×			×	
Pregnancy test	×												
Ophthalmological Examination	×	Ophthalmic examination performed within 48 hours as clinically indicated											
Vital signs ^d	×	×	×	×	×	×	×	×	×				
Clinical chemistry/hematology/urinalysis ^d	×	×	×	×	×	×	×	×	×				

• Study Plan for Randomized Treatment												
Visit ^a	Screening Period	Treatment Period							Study Discontinuation Follow-up	Follow-up Period		
		1	2	3	4	5	6	7-9		28-day follow-up ^b	Progression Follow-up Every 6/12 weeks	Survival Follow-up Every 6 weeks
Treatment cycle ^c /day		C1 D1	C1 D8	C1 D15	C2 D1	C3 D1	C4-C6 D1	D1 of C7 and Every 6/12 weeks thereafter	NA	NA	NA	NA
Day	-28	1	8	15	22	43	64-106	127+	NA	NA	NA	NA
Window period (days)	NA	0	±2	±2	±2	±7	±7	±7	+7	NA	±7	±7
Electrocardiogram ^e	×	×	×	×	×	×	×	×	×			
Echocardiography (LVEF)	×	Every 12 weeks from the first dose and as clinically indicated						×				
Collection of tumor and/or blood samples at disease progression during the randomized treatment phase (optional)									×			
Tumor assessment (RECIST v1.1) ^f	×	Every 6 weeks ± 7 days (first 15 months; C1 to C21)/every 12 weeks (after Month 15; C23 and thereafter) after randomization										
Drug dispensing		×			×	×	×	×				
Drug intake		Dosing everyday										
Concomitant medications	↔									×	Occurring prior to completion of 28-day follow-up	
Adverse Event	↔											
Anti-tumor therapy	×									×	×	
Subsequent response/progression data ^g											×	
Survival status ^h											×	

• Study Plan for Randomized Treatment												
Visit ^a	Screening Period	Treatment Period							Study Discontinuation Follow-up	Follow-up Period		

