#### 2.2.8.1. Main efficacy data

The primary endpoint of this study is the time outcome variable. When tumor efficacy assessment results are missing from a visit point, refer to [Table 4.1-2](#) and [Table 4.2-1](#) for the handling rules.

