14.2 Efficacy evaluation
14.2.1 Analysis based on endpoint PFS as evaluated by the investigator (primary event censoring rules)-full analysis set
Table 14.2.1.1 Statistical analysis based on PFS as evaluated by the investigator (primary event censoring rules)-full analysis set
Figure 14.2.1.1 Kaplan-Meier curve based on PFS as evaluated by the investigator (primary event censoring rules)-full analysis set
14.2.2 Analysis based on endpoint PFS as evaluated by the investigator (primary event censoring rules and considering primary drug resistance)-full analysis set
Table 14.2.2.1 Statistical analysis based on PFS as evaluated by the investigator-full analysis set (excluding subjects with primary drug resistance)
Figure 14.2.2.1 Kaplan-Meier curve based on PFS as evaluated by the investigator-full analysis set (excluding subjects with primary drug resistance)
14.2.3 Analysis based on endpoint PFS as evaluated by the investigator (primary event censoring rules)-per-protocol set
Table 14.2.3.1 Statistical analysis based on PFS as evaluated by the investigator (primary event censoring rules) - per-protocol set
Figure 14.2.3.1 Kaplan-Meier curve based on PFS as evaluated by the investigator (primary event censoring rules)-per-protocol set
14.2.4 Analysis based on endpoint PFS as evaluated by the investigator (secondary event censoring rules)-full analysis set
Table 14.2.4.1 Statistical analysis based on PFS as evaluated by the investigator (secondary event censoring rules)-full analysis set
Figure 14.2.4.1 Kaplan-Meier curve based on PFS as evaluated by the investigator (secondary event censoring rules)-full analysis set
14.2.5 Analysis based on endpoint PFS as evaluated by the IRC (primary event censoring rules)-full analysis set
Table 14.2.5.1 Statistical analysis based on PFS as evaluated by the IRC (primary event censoring rules)-full analysis set
Figure 14.2.5.1 Kaplan-Meier curve based on PFS as evaluated by the IRC (primary event censoring rules)-full analysis set
14.2.6 Analysis based on endpoint PFS as evaluated by the investigator (primary event censoring rules and considering the impact of the COVID-19 epidemic)-full analysis set

Table 14.2.6.1 Statistical analysis based on PFS as evaluated by the investigator (primary event censoring rules and considering the impact of the COVID-19 epidemic)-full analysis set

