Figure 14.2.6.1 Kaplan-Meier curve based on PFS as evaluated by the investigator (primary event censoring rules and considering the impact of the COVID-19 epidemic)-full analysis
14.2.7 Analysis based on endpoint PFS as evaluated by the investigator (primary event censoring rules and considering changes in the assessment cycle)-full analysis set
Table 14.2.7.1 Statistical analysis based on PFS as evaluated by the investigator (primary event censoring rules and considering changes in the assessment cycle)-full analysis set
Figure 14.2.7.1 Kaplan-Meier curve based on PFS as evaluated by the investigator (primary event censoring rules and considering changes in the assessment cycle)-full analysis set
14.2.8 Subgroup analysis based on PFS as evaluated by the investigator (based on the primary event censoring rules)-full analysis set
Figure 14.2.8.1 Forest plot of subgroup analysis based on PFS as evaluated by the investigator (based on the primary event censoring rules)-full analysis set
14.2.9 Subgroup analysis based on PFS as evaluated by the investigator (based on the primary event censoring rules) by EGFR gene mutation type-full analysis set
Figure 14.2.9.1 Kaplan-Meier curve of subgroup analysis based on PFS as evaluated by the investigator (based on the primary event censoring rules) by EGFR gene mutation type-
14.2.9a Subgroup analysis based on PFS as evaluated by the investigator (based on the primary event censoring rules) by EGFR gene mutation type-full analysis set
Figure 14.2.9.1a Kaplan-Meier curve of subgroup analysis based on PFS as evaluated against IRC (based on the primary event censoring rules) by EGFR gene mutation type-full analysis set
14.2.10 Subgroup analysis based on PFS as evaluated by the investigator (based on the primary event censoring rules) by brain metastasis status-full analysis set
Figure 14.2.10.1 Kaplan-Meier curve of subgroup analysis based on PFS as evaluated by the investigator (based on the primary event censoring rules) by brain metastasis status-
14.2.10a Subgroup analysis based on PFS as evaluated by the investigator (based on the primary event censoring rules) by brain metastasis status-full analysis set
Figure 14.2.10.1a Kaplan-Meier curve based on PFS as evaluated by the IRC (primary event censoring rules) by brain metastasis status-full analysis set

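### Two PFS sensitivity analyses in SAP 4.2 need correcting: one repeats the primary analysis, and the 42-day shift starts one scan too early (minor)

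*SAP*

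**What the plan says.** **Censoring rules.** SAP 4.1 defines the primary analysis as investigator-assessed PFS in the full analysis set (FAS) under the primary censoring rules of Table 4.1-2. The fourth bullet of SAP 4.2 reads "The primary event censoring rules are used for re-analysis of the main efficacy endpoint based on the full analysis set". Table 4.2-1, directly below the bullets, sets out secondary rules. They drop two rows of Table 4.1-2: censoring when treatment stops or new systemic therapy starts, and censoring after two or more consecutive missing or unevaluable visits. SAP 2.2.8.1 relies on both tables ("When tumor efficacy assessment results are missing from a visit point, refer to" Tables 4.1-2 and 4.2-1). Item 14.2.4 of the output list is "Analysis based on endpoint PFS as evaluated by the investigator (secondary event censoring rules)-full analysis set".

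**42-day shift.** The third bullet analyses PFS "minus 42 days of patients with disease progression after 15 months in the full analysis set". Its purpose appears only in the output list, at 14.2.7: "primary event censoring rules and considering changes in the assessment cycle". SAP 2.2 sets one month at 30.4375 days.

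**Scan schedule.** Protocol 6.1 has scans every two 21-day cycles until C21 and then "every 12 weeks (every 4 cycles starting from C23; after Month 15". The Appendix B table agrees: "every 12 weeks (after Month 15; C23 and thereafter) after randomization". Protocol 10.2.1 allows one week either side. Note f to the Appendix B table and section 4.1 of Appendix D give a 6-week interval with no 12-week phase.

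**The concern.** A sensitivity analysis has to change something. The fourth bullet names the same endpoint, population and rules as the primary analysis, so read literally it tests nothing. The check that counts events after treatment stop, new therapy or missed visits is missing from the text of 4.2. That check matters because Protocol 12.1.3 requires scans to continue to progression in exactly those patients.

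The shift is meant to remove the extra delay in detecting progression once scans move from 6 to 12 weeks apart. Subtracting 42 days from a progression found after an 84-day gap places it at the midpoint of the gap. Subtracting 42 days after an ordinary 42-day gap places it on the previous scan, at which the patient was progression-free. If the 15-month cut-off catches a scan of the second kind, the table mixes a sound correction with a dating error. The scan in question lies beside the planned HS-10296 median of 15 months.

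**Working it through.** **Fourth bullet: bullets against outputs.**

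| SAP 4.2 bullet | Output |
|---|---|
| 1. Early progressors removed | 14.2.2 |
| 2. Per-protocol set | 14.2.3 |
| 3. 42-day shift | 14.2.7 |
| 4. FAS, *primary* rules | 14.2.4, FAS, *secondary* rules |
| 5. IRC assessment | 14.2.5 |
| 6. Epidemic-related NE | 14.2.6 |

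The match is one to one, and only the fourth pair disagrees. No output repeats the primary analysis.

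**Shift: calendar.** Day 1 of cycle n is 1 + 21(n − 1). This reproduces the days that SAP Table 2.2.6-1 gives for C21 and C23.

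- C21: 1 + 21 × 20 = day 421
- C23: 1 + 21 × 22 = day 463, a gap of 42 days
- C27: 1 + 21 × 26 = day 547, a gap of 84 days
- Cut-off: 15 × 30.4375 = day 456.6

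C23 falls after the cut-off, so its progressions are shifted: 463 − 42 = 421, the C21 scan. At C27, 547 − 42 = 505, the midpoint of 463 and 547, as intended.

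**Windows.** With ±7 days the C23 scan falls on days 456 to 470. Day 456 is not shifted; days 457 to 470 are, to days 415 to 428. If both scan days are independent and uniform over their windows (assumption), the number of day pairs in which the shifted date is on or before the patient's own C21 scan is 14 + 13 + … + 1 = 105 of 14 × 15 = 210, or 0.50.

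**How many patients.** Planning inputs (SAP 1.2.3): medians 10 and 15 months, 410 patients 1:1, 8 months' accrual (taken as uniform), 23 months in total, exponential PFS.

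- Probability of progressing between C21 and C23 (420 and 462 days elapsed): gefitinib 0.0350, HS-10296 0.0326.
- Share followed to C23: (23 − 15.18)/8 = 0.978.
- Expected C23 progressions: 205 × 0.978 × (0.0350 + 0.0326) = 13.6, against about 21.6 at later scans.

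With scan windows, simulation gives about 12.6 to 12.9 of about 34 shifted events.

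**Why the median can move.** Expected HS-10296 PFS is 0.5^(420/456.6) = 0.528 at C21 and 0.5^(462/456.6) = 0.496 at C23. The curve is expected to cross 0.5 at C23 when the true median lies between 420/30.4375 = 13.8 and 462/30.4375 = 15.2 months.

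**Simulation.** 2,000 trials per setting under the planning inputs; scans every 42 days to C23, then every 84; no separate deaths or dropout; unstratified Cox model with Efron ties; about 258 events. Corrected means that only progressions found after C23 are shifted.

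| True HS-10296 median 15 months | No shift | As written | Corrected |
|---|---|---|---|
| HR, ±7-day scans | 0.668 | 0.667 | 0.667 |
| HR, exact dates | 0.666 | 0.666 | 0.666 |
| Estimated median, mean over trials, ±7-day | 15.9 | 15.2 | 15.5 |
| Estimated median, mean over trials, exact | 16.2 | 15.1 | 15.6 |
| Estimated median, median over trials, ±7-day | 15.3 | 14.1 | 15.3 |
| Estimated median, median over trials, exact | 15.2 | 13.8 | 15.2 |

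The as-written median is at least 0.5 months below the corrected one in about 30 to 35% of trials and at least 0.5 months above it in about 0 to 10%. With a true median of 18.9 months (the figure Protocol 4.3.2 cites for osimertinib), the two differ by less than 0.2 months on either summary.

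**The case against.** **The output list already settles the fourth bullet.** Item 14.2.4 states the secondary rules and the FAS in full, so a programmer working from the list would run the right check. This stands. A reader might infer that the secondary-rule analysis would never be done; the documents do not support that. What remains is a wrong word in the governing text.

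**The shift finding depends on a scan at C23.** If the scan after C21 were at C25 (day 505), the gap would be 84 days, 505 − 42 = 463 would be its midpoint, and the 15-month cut-off would be right. Protocol 6.1 and the Appendix B table both point to a scan at C23, so that is the natural reading. But note f and Appendix D 4.1 do not describe a 12-week phase at all, and the finding is conditional on this point.

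**The effect on the median is easily overstated.** A reader might infer that the table will report a median 1.3 to 1.4 months too low. That figure is a jump between adjacent scan dates on a step function. On the mean over trials the difference is 0.3 to 0.5 months, and there the as-written estimate (15.1 to 15.2) is nearer the assumed 15 months than the corrected one (15.5 to 15.6), because scan-detected progression is late in any case. This stands too. The argument for the change is that the rule misdates a definable group of patients, not that it gives a more biased median.

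**Visits alone do not cover every case.** Table 4.1-2 counts progressions found at unplanned visits. A C23 progression after a missed C21 scan also follows an 84-day gap (C19 is day 379). A rule that names only scheduled visits would leave both undefined.

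**Conclusion.** Both corrections are warranted, at minor severity. As written, the fourth bullet duplicates the primary analysis and contradicts output 14.2.4. The 42-day shift begins one scan early if a scan takes place at C23, and its cut-off also splits the C23 window. About 13 to 14 expected progressions are affected under the planning assumptions. The consequence is confined to the Kaplan-Meier curve and HS-10296 median of one sensitivity table. The median can drop from about 15.2 to 13.8 months in some trials if the true median is near 15 months; the effect is small on average and negligible at 18.9 months.

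A reader might infer that the primary result or the hazard ratio is at risk. Neither is: the primary test, alpha, 262 events and 410 patients do not depend on these bullets, and the simulated hazard ratios agree to within 0.001.

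A reader might also count the epidemic bullet, whose subjects "are censored to the date on which the evaluation result before disease progression is" NE, as a third error. SAP 2.2.9 states the same rule, so it is a deliberate choice and not part of this point.

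**What to change.** 1. In the fourth bullet of SAP 4.2, replace the primary rules with the secondary event censoring rules (Table 4.2-1), to match output 14.2.4.
2. Define the 42-day shift by the preceding scan interval, not by month: apply it only to progressions first found after a scheduled 12-week interval, that is after the C23 scan, so from C27 onward. State how progressions found at unscheduled scans, and C23 progressions after a missed C21 scan, are handled.
3. Reconcile note f of the Appendix B table and Appendix D 4.1 with Protocol 6.1, so that it is explicit whether a scan takes place at C23. The second change rests on this.

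The cost is SAP and protocol wording and a few lines of programming, with no new data. The SAP changes should be made before the data are locked, the point by which SAP 2.2 requires the plan to be final.
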